To date, no studies have explored treatment options for non-daily smokers and, as a result, treatment guidelines are not available to guide patients or healthcare providers. The study will compare two treatments -- smoking cessation counseling alone versus counseling in combination with patients' choice of nicotine patch, gum, or lozenge -- on their effects on quitting smoking and reducing exposure to nicotine and cancer causing agents. Findings will identify which patients are most likely to benefit from each form of treatment (counseling, nicotine gum, patch, or lozenge) and will allow patients and providers to estimate their chances of success based on personal characteristics – for example, age, gender, level of smoking – and the treatment they chose. This study will determine if NRT is safe and effective for AA non-daily smokers. The program will be the first to examine treatment options for non-daily smokers and could directly contribute to the first evidence-based guidelines for treating the 9.7 million U.S. adult non-daily smokers for whom no guidelines currently exist.

[figure not shown]
II. RESEARCH PLAN AND DESIGN

A. Study Objectives

The objective of this study is to examine if NRT is an effective treatment option for AA non-daily smokers. Outcomes will be measured at weeks 12 and 26 and will include biologically confirmed smoking abstinence, nicotine intake, carcinogen exposure, days abstinent, NRT adherence and side effects.

B. Study Type and Design:

The proposed study is a randomized trial of 384 AA non-daily smokers randomized to receive either 5 sessions of smoking

Projected sample size by group using 2:1 randomization, whereby 67% are randomized to C+NRT and 33% are randomized to C

cessation counseling in combination with 12 weeks of nicotine patch, gum, or lozenge (C+NRT) or 5 sessions of smoking cessation counseling alone (C). We will use 2:1 randomization; for every patient randomized to C, two will be randomized to C+NRT (see Figure). The primary outcome is biologically-confirmed 7-day abstinence from smoking at 12 weeks. Patient- and provider-driven secondary outcomes include reductions in nicotine intake and carcinogen exposure, days abstinent, NRT adherence and side effects. Participants will be recruited from the University of Kansas Medical Center (KUMC) and Swope Health Central, a community-based primary care clinic in urban Kansas City that serves a predominately AA clientele.

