C. Sample size, statistical methods, and power calculation

384 AA non-daily smokers will be randomized. We will use 2:1 randomization; for every patient randomized to C, two will be randomized to C+NRT (see Figure). Randomization will be determined by computer-generated random numbers generated by [name]. Randomization assignments will be placed in sealed envelopes by a member of [name] team with sequential study ID numbers. After baseline data collection has been completed, the research assistant will select the sequential study ID number from the sealed envelope to determine the randomization assignment.

The maximum number of participants enrolled in C will be 128 and the maximum number enrolled in C+NRT will be 256. Our sample size is based on our primary outcome, biochemically confirmed point-prevalence abstinence at Week 12 using an intent-to-treat approach. Based on treatment studies with AA light smokers who have received tobacco treatment guideline-based counseling and no pharmacotherapy, we expect a 10% point prevalence abstinence rate in the C group and a 20-25% point prevalence abstinence rate in the C+NRT group based on recent meta-analyses and studies examining the effectiveness of these medications in AA light smokers.^{11,28,45,46} Using the chi-square test, along with the assumptions above, 256 participants in the C+NRT group and 128 participants in the C group (n=384), we will have 95% power to detect an increase from 10% to 25% in cessation at Week 12 between C and C+NRT, 87% power to detect a and increase from 10% to 22.5%, and 71% power to detect an increase from 10% to 20% with a type 1 error rate of 5%.

Analysis Plan for Each Aim

All primary analyses on smoking cessation will be conducted using intent-to-treat and will code those lost to follow-up as smokers. Subsequently we will evaluate the missing data pattern. If there is a differential loss based upon group, multiple imputation techniques will also be used.

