Specific Aim 2: To compare patient- and provider-desired outcomes -- e.g., nicotine intake, carcinogen exposure, number of days abstinent, and side effects – among AA non-daily smokers receiving C versus C+NRT and, within the C+NRT group, examine the choice of NRT and use during the treatment period. Hypothesis: Participants randomized to C+NRT will demonstrate significantly greater reductions in nicotine intake and carcinogen exposure and significantly more days abstinent, while experiencing no differences in side effects as participants randomized to C. Analytic strategy: We will utilize linear mixed models to longitudinally (week 12 and 26) compare nicotine and carcinogen exposure between the two groups, then subsequently examine the effects of the covariates listed in the measurement table above using a best subsets selection method for both nicotine and carcinogen exposure independently. A generalized linear mixed model approach will be used to model days abstinent, controlling for number of days in study, to assess the effect of treatment on this endpoint and best subsets selection will be used to examine the effects of covariates on this endpoint. For each of these models, based upon the sample size, we anticipate that ten to twelve covariates could be included in a final model. We will compare the prevalence of any side effect as well as each specific side effect, from baseline to week 12, between the two groups using the chi-square test. If there is a global difference we will examine, within the NRT group, if type of NRT impacts the side effect profile. Within the NRT group we will descriptively summarize the number and percent of subjects who choose each type of NRT. Subsequently we will describe and descriptively compare the percent of subjects within each of these subgroups who use the NRT of choice during the treatment period (i.e., percent of patients within the patch, gum, and lozenge groups who used the medication).

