Specific Aim 3: Identify subgroups of AA non-daily smokers for whom the relative benefits of treatment might differ. We will employ a Classification and Regression Tree decision tree modeling on Week 12 verified smoking status (quit versus not quit) to identify subgroups of participants whose personal characteristics might impact the benefit of treatment. The resulting decision tree will allow smokers and their providers to estimate their individual chances of success given their choice of treatment. To maximize the utility of the decision tree, we solicited input from our Stakeholder Advisory Committee and Patient Advisory Panel and included the demographic, smoking, and treatment-related variables identified by them (see Measures and Time Points Table) for possible inclusion in the predictive model. The candidate variables, along with treatment assignment (C, C+NRT) will be entered into a recursive partitioning model as described by Brieman and Freidman using the RPART package in the R statistical software.⁴⁷ Specific methods related to building the tree (using appropriate splitting criteria and loss incorporation using the altered priors method), pruning the tree and handling missing data (using surrogate variables) will be deployed using the techniques described by Therneau et al.⁴⁸ Given the cessation rate expected and overall sample size, a validation subsampling scheme will not be feasible, thus we will utilize 10-fold cross-validation on the regression tree to assess its properties. Additionally, we will account for the uncertainty in tree classification by

generating a bootstrap sampling distribution of the predictive as described by Shalizi.⁴⁹ Modeling cessation was of greatest interest for our initial Patient and Stakeholder Advisory Panels, but other outcomes (reduction in nicotine or carcinogen exposure) could be modeled if our patients and stakeholders think that these additional models might be useful.

D. Subject Criteria (See Vulnerable Populations appendix, if applicable)

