Counseling Visits (Wks 0,1,4,8,10). Counseling sessions will be completed by phone at Wks 1,4, 8,10, and in person at Wk 0. The number of sessions is consistent with our previous studies where we have achieved visit completion rates of around 80%.^{45,55,56}

NRT Dispensing (Wks 0-1). Participants randomized to C+NRT will be given a trial supply of nicotine gum, patch, and lozenge and be instructed to try each for 3-days. After the 3 to 9-day trial period, they will select and be mailed a 4 week supply of the medication of their choice. They will receive refills of their selected medication at the Weeks 4 and 8 study visits.

Biological Sample Collection (Wk 0,12,26). Urine will be collected three times throughout the study for biochemical verification of cessation at Wk 12 and Wk 26, nicotine intake at Wks 0, 12, 26, and carcinogen exposure at Wks 0, 12, and 26. Additional details regarding each assay are provided in the Measures and Assessment Time Points table.

Retention. We have developed a system of reminders and compensation that have resulted in impressive retention rates in our previous clinical trials. Reminders. One week prior to each scheduled visit a reminder postcard noting the scheduled appointment date and time will be mailed to participants. In addition, participants will be called up to 6 times to remind them of their upcoming visit. A detailed tracking database, with an automated reminder system, will notify counselors of when to send postcards and complete reminder phone calls. Compensation. Participants will be given a \$40 electronically loaded gift card at Wks 0, 12 and a \$20 electronically loaded gift card at Wks 1, 4, 8, 10, 26 in appreciation for their time and participation.

Measures

Our selection of measures (see table) and the measurement time points have been driven by our patient and stakeholder advisory panels.

Measure and Assessment Time Points

Primary Scientific Outcome (Aim 1)

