Smoking abstinence at Wk 12 (primary cessation outcome) and Wk 26 (secondary cessation outcome). Biochemically confirmed at Wk 12 using urine anabasine and anatabine, with the recommended cut-off of 2 ng/ml to differentiate smokers from non-smokers. ⁵⁰ These tobacco alkaloids are considered the gold standard for confirming abstinence when cotinine measurements are not valid – i.e., detectable levels of cotinine could reflect NRT use or smoking. ⁵⁰ Biochemically confirmed at Wk 26 using urinary cotinine, the proximate metabolite of nicotine, with the recommended cut-off of 50 ng/ml used to differentiate smokers from non-smokers. ⁵¹ Time Points: Wk 12, 26
Secondary Patient- and Provider-Derived Outcomes (Aim 2)
Nicotine intake (total nicotine equivalents/creatinine). Assessed by urine; quantified by examining the sum of four of the major nicotine metabolites (cotinine + cotinine-glucuronide + trans-3'-hydroxycotinine + 3HC-glucuronide) to creatinine ratio using procedures described by [name] (consultant). ⁵¹ Total nicotine equivalents/creatinine represents the current gold standard for estimating nicotine intake/exposure from tobacco. ⁵⁷ To ensure that nicotine metabolites detected at Wk 12 are a result of tobacco exposure and not NRT use, we will schedule the urine collection for 7 days after the last dose of NRT. This 7-day time frame is more than adequate given the 15-20 hour (3-4 day) elimination half-life of cotinine and accounts for the substantial individual variability in the rate of elimination of nicotine. ⁵⁸ Time Points: Wks 0,12,26
Carcinogen exposure [NNAL, PAH]. Assessed by urine; quantified by examining NNAL (4-(methylnitrosamino)-1-(3)pyridyl-1-butanol) and polycyclic aromatic hydrocarbons (PAH) and specifically, 1-hydroxypyrene (1-HOP), using procedures described by [name] (consultant). ⁴⁰ While there are >70 established carcinogens in tobacco, NNAL and PAH are widely considered to be among the most important causative agents in the development of lung and esophageal cancer ^{38,39,59} and reflect the current gold standard for estimating carcinogen exposure from tobacco products. Time Points: Wks 0,12,26
Days Abstinent. Cumulative number of days abstinent Time Points: Wks 1,4,8,10,12
NRT adherence. 3-day recall of NRT use (C+NRT only) -- i.e., pieces of gum, lozenge, or number of patches used in the last 3 Time Points: Wks 4,8,12

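### The Aim 2 biomarker mixed model gives the collected Week 0 value no stated role; adjusting for it would cost nothing in data and gain precision

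*Combined protocol and SAP*

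**What the plan says.** The Aim 2 hypothesis (section II.C) is that "Participants randomized to C+NRT will demonstrate significantly greater reductions in nicotine intake and carcinogen exposure". Section II.B uses the same idea: "Patient- and provider-driven secondary outcomes include reductions in nicotine intake and carcinogen exposure, days abstinent, NRT adherence and side effects". Specific Aim 3 refers back to it: "other outcomes (reduction in nicotine or carcinogen exposure) could be modeled".

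Section II.E, Biological Sample Collection, schedules urine for "nicotine intake at Wks 0, 12, 26, and carcinogen exposure at Wks 0, 12, and 26". The Laboratory Tests text and the Measure and Assessment Time Points table give the same three visits.

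The only model for these markers is in Specific Aim 2: "We will utilize linear mixed models to longitudinally (week 12 and 26) compare nicotine and carcinogen exposure between the two groups". A second step will then "examine the effects of the covariates listed in the measurement table above using a best subsets selection method". The covariates in that table fall under demographics, self-reported smoking history and treatment; none is a urine marker.

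On timing, section II.C says: "After baseline data collection has been completed, the research assistant will select the sequential study ID number" from a sealed envelope to learn the assignment.

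**The concern.** A reduction is measured from a starting value. The model names two follow-up visits and is silent on the starting value, although it is collected for every marker. Four analyses fit the text:

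- follow-up level alone, which is the literal reading;
- change from Week 0;
- follow-up level adjusted for Week 0;
- a model with Week 0 as a further outcome row.

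These differ in precision, and the choice could be made after the data are seen. Elsewhere in the same Aim 2 paragraph the plan does say when it adjusts or uses a baseline: the days-abstinent model controls for time in study, and side effects are compared from baseline to Week 12. The biomarker sentence has neither.

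At stake is the precision of the nicotine-intake and carcinogen comparisons, and whether their analysis is fixed in advance. The primary abstinence test is not involved.

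**Working it through.** **The plan's own power figures.** The only power figures are for Week 12 abstinence (section II.C): 128 in C, 256 in C+NRT, 10% against 25%, 22.5% and 20%, type 1 error 5%. A two-sided chi-square calculation with pooled null variance and no continuity correction gives 95.7%, 87.6% and 71.7%, in line with the stated 95%, 87% and 71%. No power is stated for the biomarkers.

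**Inputs for Aim 2.** Arm sizes come from section II.C. The rest are assumptions, because the documents do not give them: r = 0.2 to 0.7 and a treatment difference of 0.30 SD. A second scenario assumes 80% provide urine (102 and 205, total 307). That rate is borrowed from the counselling-visit completion of around 80% in section II.E.

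**Formulas** (one visit, two-sided 5%, normal approximation, SD units):

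- SE, level alone = √(1/128 + 1/256) = 0.108; with 307, √(1/102 + 1/205) = 0.121.
- Adjusting for Week 0 multiplies the variance by 1 − r², so the equivalent total is 384/(1 − r²).
- Power = Φ(0.30/SE − 1.96). Level alone: 0.30/0.1083 − 1.96 = 0.81, giving 79%; with 307, 70%.
- Difference detectable with 80% power, level alone: (1.96 + 0.84) × 0.1083 = 0.303 SD.

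| r | 1 − r² | Equivalent N | Power, 384 | Power, 307 | Detectable at 80%, 384 (SD) |
|---|---|---|---|---|---|
| level alone | 1.00 | 384 | 79% | 70% | 0.303 |
| 0.2 | 0.96 | 400 | 81% | 71% | 0.297 |
| 0.3 | 0.91 | 422 | 83% | 74% | 0.289 |
| 0.5 | 0.75 | 512 | 89% | 82% | 0.263 |
| 0.7 | 0.51 | 753 | 97% | 93% | 0.217 |

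Simulation (4,000 runs per setting, complete data) gave level-alone bias of about zero, type I error of 4.3% to 5.5% and a mean SE of 0.108. The adjusted SEs were 0.103, 0.094 and 0.077 at r = 0.3, 0.5 and 0.7, which match √(1 − r²).

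**Both follow-up visits together.** If all three visits share one correlation r, the average of Weeks 12 and 26 has variance (1 + r)/2 for level alone and (1 + r)/2 − r² adjusted. The ratios are 0.86, 0.67 and 0.42 at r = 0.3, 0.5 and 0.7, so the single-visit figures do not overstate the gain.

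**Change score.** With k = SD at Week 0 divided by SD at follow-up, its variance relative to level alone is 1 + k² − 2rk = (1 − r²) + (k − r)². In large samples this is never below the adjusted value, and it exceeds 1 when r < k/2. For r = 0.2, 0.3, 0.5 and 0.7 it is 1.60, 1.40, 1.00 and 0.60 with equal SDs, and 1.18, 1.04, 0.78 and 0.51 if the follow-up SD is 1.5 times the Week 0 SD (an illustration). A plain change score, a natural reading of the hypothesis, can therefore be worse than ignoring Week 0.

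**Chance imbalance.** The Week 0 difference between arms also has SE 0.108 SD, so it exceeds 0.1 SD in about 36% of randomisations and 0.2 SD in about 6%. A 0.2 SD imbalance moves a level-only estimate by r × 0.2 = 0.04, 0.06, 0.10 or 0.14 SD at the four values of r. This is the same variance that 1 − r² removes, seen in a single trial; it is not an additional loss.

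**The case against.** The strongest reply is that this is a gap in wording. The two named weeks can be read as the visits at which arms are compared, with Week 0 as an implied reference, and the text does not exclude Week 0. If the team already means to adjust, nothing is lost. That is fair, but no sentence says so, and the text fits other choices equally well.

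The size is also unknown. At r of 0.3 or less the power gain is under 4 points with 384 analysed. Low r is plausible: eligibility allows smoking on 4 to 27 of 30 days, and the measures table gives cotinine a short half-life ("This 7-day time frame is more than adequate given the 15-20 hour (3-4 day) elimination half-life of cotinine"), so one Week 0 sample may say little about a later one. This stands as a limit on the magnitude.

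The smoking-history covariates, such as days smoked per month, may partly stand in for the Week 0 marker in the later selected model, which would shrink the added gain there. That gain has not been estimated. The first treatment comparison remains unadjusted, and data-driven selection is not pre-specified adjustment.

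Finally, no sentence places the Week 0 urine itself before allocation. Section II.C puts randomisation after baseline data collection, which supports treating it as a pre-randomisation value, but the order should be confirmed.

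**Conclusion.** The concern holds. The Week 0 biomarker values have no stated role in the model that tests the reduction hypothesis, and the later covariate step does not supply one. The literal model is valid under randomisation without selective loss, but less precise than a Week 0-adjusted comparison. The single-visit variance factor runs from 0.96 to 0.51 over the assumed r of 0.2 to 0.7: slight at the low end, substantial at the high end. The documents cannot say where in that range the trial will fall.

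The condition on loss matters. In one assumed simulation, about 20% were missing and dropout depended on Week 0 in opposite directions in the two arms. The level-only single-visit comparison was then biased by 0.08 to 0.19 SD, with type I error of 10% to 35% (r = 0.3 to 0.7); the adjusted comparison stayed near 5%. This illustrates the dependence and does not predict what will happen here.

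Only secondary outcomes are affected. The primary chi-square test, the 384 participants and the stated power are untouched. The change should be made, but validity of the main result does not depend on it.

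**What to change.** In section II.C, Specific Aim 2, pre-specify that the main treatment comparison for each biomarker adjusts for the Week 0 value of the same marker, on the same scale as the outcome, and name that scale. Either form is acceptable:

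1. Week 0 as a fixed covariate, with treatment, visit and treatment-by-visit terms.
2. Week 0 as an outcome row with a mean constrained to be equal across arms. This keeps participants without a Week 0 result.

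With complete Week 0 data the two forms give the same factors (0.96, 0.91, 0.75, 0.51). If 10% of Week 0 values were missing at random (assumed, with a Week 12 to 26 correlation of at least 0.5), the second gives 0.96, 0.92, 0.77 and 0.53. The covariate form with those participants dropped gives (1 − r²)/0.9 = 1.07, 1.01, 0.83 and 0.57, so it needs a rule for missing Week 0 values.

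Do not rely on an unadjusted change score to express reductions. Confirm in the procedures that Week 0 urine is taken before allocation.

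The cost is a short addition to the analysis plan and one more model term. No new samples, visits or participants are needed.

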and an objective marker of daily nicotine exposure, and NNAL, a potent carcinogen that is independently associated with the risk of lung and esophageal cancer in large cohorts of smokers.^{38,39} Studies of daily smokers have found median cotinine levels of 1,323 ng/mg and NNAL levels of 230-300 pg/mg.^{40,41} In comparing our data (see table) to these studies, AA non-daily smokers (median of 5.0 cpd on days smoked) had an average daily cotinine intake that was 61% that of daily smokers, who smoked substantially more (11.5-17.2 cpd),^{46,47} while the average daily intake of H/L and W non-daily smokers was only 9% and 20% that of daily smokers. More striking, however, is that AA non-daily smokers are exposed to substantial amounts of the potent lung and esophageal carcinogen, NNAL, despite their low levels of cigarette consumption. By comparison, AA non-daily smokers in our study averaged 63%-82% of the intake of NNAL of daily smokers, compared to H/L and W non-daily smokers whose intake of NNAL was only 14%-28% that of daily smokers.^{35,40,41} These data are consistent with other studies indicating that, while AA smoker fewer cigarettes per day, they smoke cigarettes more intensively, extracting more cotinine and potent carcinogens per cigarette smoked.⁴²⁻⁴⁴ Together, these data suggest that AA non-daily smokers incur significant nicotine and carcinogen exposure at low levels of cigarette consumption and make the treatment of AA non-daily smokers a critical but overlooked area.

Significance

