Participants will be AA adults over the age of 18 who smoked on 4-27 days out of the past 30 at enrollment and have smoked at this non-daily rate for ≥ 3 months. The study will be open to both men and women. We have chosen to focus on AAs only because their unique smoking profile places them at greater risk for tobacco-related disease and death^{44,45,50-52} Importantly, this study represents a starting point for future work that can be expanded to other ethnic groups with high rates of non-daily smoking.

Inclusion Criteria

Inclusion criteria are displayed in the adjoining table. Participants must have smoked 100 cigarettes or little cigars in their lifetime to ensure that

they are smokers and to have smoked at their current rate for ≥ 3 months to avoid enrolling smokers who are in the transitory stages of smoking initiation or reduction/cessation.

Participants also cannot be daily users of other tobacco products, not including e-cigarettes. Other racial groups will be excluded as our primary aim is to evaluate NRT in AA smokers.

Eligibility Criteria

Inclusion Criteria	Exclusion Criteria

 • African American ≥ 18 years of age • Smoke 100 lifetime cigarettes • Smoke cigarettes or little cigars on 4-27 days of the past 30 days • Smoke cigarettes or little cigars at current rate for ≥ 3 months • Use of any tobacco product, not including e-cigs, on 4-27 days in last 30 • Functioning telephone • Interested in quitting smoking • Willing to take NRT for 12 weeks and complete all study procedures 	
 • Unstable cardiac condition (e.g., unstable angina or AMI in the past 4 weeks) • Plans to move from KC during the treatment and follow-up phase • Use of pharmacotherapy, including e-cigs, in the month prior to enrollment • Pregnant or breastfeeding • Another household member enrolled in the study • Unstable housing (e.g., homeless, drug/alcohol treatment center)

Exclusion Criteria

Exclusion criteria are also displayed in the adjoining table. Exclusion criteria are consistent with contraindications for nicotine gum, patch, and lozenge.¹¹

Withdrawal/Termination Criteria

There are no expected circumstances in which the subject’s participation will be terminated by the investigator.

Clarify whether a study subject may participate in another research study while participating in this research study

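### Aim 2 names linear mixed models for the nicotine and carcinogen biomarkers without fixing the analysis scale, a rule for values below the assay limit, or a Week 0 term

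*Combined protocol and SAP*

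**What the plan says.** Section II.C, Specific Aim 2: "We will utilize linear mixed models to longitudinally (week 12 and 26) compare nicotine and carcinogen exposure between the two groups". Best subsets selection of covariates follows, for nicotine and carcinogen exposure separately. The hypothesis is directional: "Participants randomized to C+NRT will demonstrate significantly greater reductions in nicotine intake and carcinogen exposure and significantly more days abstinent". In the same paragraph days abstinent gets a generalized linear mixed model, so the plan does vary the model by outcome.

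The measures table in section II.E defines nicotine intake as the sum of four urinary metabolites divided by creatinine, and says of it: "Total nicotine equivalents/creatinine represents the current gold standard for estimating nicotine intake/exposure from tobacco". Carcinogen exposure is urinary NNAL and 1-HOP. All are measured at Weeks 0, 12 and 26. The Week 12 urine is timed 7 days after the last NRT dose so that nicotine metabolites reflect tobacco.

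For quit rates, the sample size section says "we expect a 10% point prevalence abstinence rate in the C group and a 20-25% point prevalence abstinence rate in the C+NRT group".

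Nowhere does the text give a transformation, a distributional check, an SD or CV, an LOQ or a rule for values below it, a Week 0 term in these models, or power for these outcomes. The 2 ng/ml and 50 ng/ml cut-offs classify abstinence; they are not quantification limits.

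**The concern.** The outcomes cannot be negative, and verified quitters should lie near the bottom of the range. Entry is open to people who "smoked on 4-27 days out of the past 30 at enrollment", a 27/4 = 6.75-fold range in smoking days before cigarettes per smoking day or metabolism vary. The background summarises other cohorts by medians: "Studies of daily smokers have found median cotinine levels of 1,323 ng/mg and NNAL levels of 230-300 pg/mg". Neither fact measures the spread in this trial, but both make a wide, right-skewed distribution plausible.

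An untransformed model compares arithmetic means. A light smoker who quits moves that mean by no more than his or her own small level, whereas on the log scale the same quit counts as a large proportional fall. If the raw scale is used, the Aim 2 hypothesis could be missed while the cessation effect is present. If the scale stays open, it can be chosen after the data are seen, for three biomarkers, and the result can depend on the choice. The LOQ rule matters most on the log scale, where any substituted value decides how far down the quitters sit.

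**Working it through.** **1. The plan's own figure.** The section claims "71% power to detect an increase from 10% to 20% with a type 1 error rate of 5" per cent, with 128 in C and 256 in C+NRT. Pooled rate = (12.8 + 51.2)/384 = 0.1667. SE under the null = √[0.1667 × 0.8333 × (1/128 + 1/256)] = 0.0403. SE under the alternative = √(0.09/128 + 0.16/256) = 0.0364. Power = Φ[(0.10 − 1.96 × 0.0403)/0.0364] = 71.7%. The other two stated figures, 95% and 87%, come out at 95.7% and 87.6%. So the stated power is two-sided and sound. It covers abstinence only.

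**2. Inputs for the biomarkers.** From the documents: 128 and 256 participants; quit rates 10% versus 20-25%; visits at Weeks 12 and 26. Assumed, because the documents are silent: lognormal levels in smokers with between-person log SD *s*; quitters at a fraction *f* of their own usual level; the same quit status at both visits; no dropout.

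**3. Closed form, one visit, no baseline.** With quit proportion *q*:

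- Raw mean = exp(s²/2) × [1 − q(1 − f)]; raw second moment = exp(2s²) × [1 − q(1 − f²)].
- Log mean = q ln f; log variance = s² + q(1 − q)(ln f)².

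Example with s = 1.0, f = 0.10, 10% versus 20% quits:

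- Raw: means 1.500 and 1.352, variances 4.407 and 4.098. SE = √(4.407/128 + 4.098/256) = 0.2246; z = 0.1484/0.2246 = 0.661; power = Φ(0.661 − 1.960) = 9.7%.
- Log: difference 0.10 × ln 0.10 = −0.2303, variances 1.477 and 1.848. SE = √(1.477/128 + 1.848/256) = 0.1370; z = 1.681; power = Φ(1.681 − 1.960) = 39.0%.

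Over residuals of 2-20%, raw versus log is 26-33% versus 52-73% at log SD 0.5, 9-11% versus 26-59% at 1.0, and about 5% versus 15-44% at 1.5.

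**4. Why raw power is low.** A 10-point quit difference shifts the raw mean by 0.10 × (1 − f), which is 8.0% of the smoker mean at f = 0.20 and 9.8% at f = 0.02. Even at the mildest spread (log SD 0.5, CV 0.53) raw power is only 26-33%. Dilution by the 80-90% who do not quit is therefore part of the cause, alongside the upper tail.

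**5. Simulation, mean of two visits, no baseline.** Within-person log SD 0.5, between-person log SD 0.6-1.3, residual 1% or 10%:

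| Effect | Raw | Log |
|---|---|---|
| 10% vs 20% quits only | 5-18% | 27-68% |
| 10% vs 25% quits only | 6-40% | 52-94% |
| 10% vs 20% quits plus a 20% cut in continuing C+NRT smokers | 24-90% | 68-96% |

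The 20% cut is an assumption. Repeat runs move single cells by several points (quits only, 1% residual, log SD 1.3: log power 41% to about 50%), so these ranges are approximate.

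**6. With the Week 0 value as covariate.** Raw power in the third row rises to 59-97%. For quits only (10% versus 20%, 1% residual), raw versus log is 26 vs 68%, 20 vs 67%, 15 vs 69% and 11 vs 64% at log SD 0.6, 0.8, 1.0 and 1.3.

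**7. The reverse case.** Suppose 10% quit in both arms and NRT cuts intake by 25% in continuing smokers (1% residual, no baseline). Raw versus log is then 82 vs 37% at log SD 0.6, 60 vs 33% at 0.8, 44 vs 34% at 1.0 and 26 vs 32% at 1.3. Hand check of the log figure at 0.6: difference 0.9 × ln 0.75 = −0.259. Variance in C = 0.36 + 0.25/2 + 0.09 × (ln 0.01)² = 2.394. In C+NRT the jump to quitter level is ln 0.01 − ln 0.75, so the variance is 0.485 + 0.09 × 4.317² = 2.163. SE = √(2.394/128 + 2.163/256) = 0.165; z = 1.57; power = Φ(1.57 − 1.96) = 35%. Most of the log-scale variance here is the quitter cluster, and a Week 0 covariate does not remove that part.

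**The case against.** A linear mixed model on log values is still a linear mixed model, and the sentence names no scale. A reader might infer that the plan prescribes the raw scale. It does not: untransformed is the literal default for outcomes defined as plain ratios or concentrations, not a stated choice. This objection stands, and the defect is one of specification.

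A reader might also infer that a few heavy smokers would set the variance and hide the quit difference almost entirely. The documents do not support that. They give no SD; the 4-27 day window is an eligibility range, and quoting medians does not prove skewness. Dilution lowers raw power too. The hypothesis concerns reductions in general, and with a 20% cut in continuing smokers raw power reaches 90% at the small-spread end, or 97% with Week 0 adjustment. Nor can it be said that the residual assumptions fail: nothing shows the data, and the quitter cluster strains normality on the log scale as well.

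Two further objections carry weight. Log-scale power depends on the quitter residual, which the documents do not give for any marker and which need not be equal across the three. And the arithmetic mean is a legitimate measure of exposure burden, so neither scale is better in every case; step 7 shows this. But a reduction with no added quits contradicts the trial's primary hypothesis.

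**Conclusion.** The point holds as a gap in specification with real consequences. Scale, LOQ rule and Week 0 term are all unstated, and the literal default performs worse than the log scale when the planned quit difference drives the effect. In the quits-only cases computed, log did better throughout, but it is no full remedy: at 10% versus 20% it stayed below 80%. When continuing smokers also cut down, the gap is small at low spread and large at high spread, and Week 0 adjustment narrows it. All of this rests on assumed lognormal spread and quitter residuals. The primary chi-square test and the sample size are untouched. It should be settled before biomarker results are examined by arm, because one of three stated aims depends on it.

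**What to change.** In the Aim 2 analysis text:

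- fit the mixed models to the log of each biomarker, with the log Week 0 value as a covariate;
- report geometric mean ratios (C+NRT to C) with 95% confidence intervals;
- state each assay's LOQ, treat values below it as left-censored, and use simple substitution only as a check;
- keep the raw-scale mean difference as a named sensitivity analysis;
- give power for these outcomes under a stated SD and quitter residual.

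The cost is SAP wording and modest programming for the censored model, with no new data or visits. The text should also state the downside: if NRT lowers intake only in continuing smokers, the log scale can lose substantial power at small between-person spread.
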